#### 6.1.2 Stability and Storage

Cisplatin is stable at controlled room temperature 15° - 25°C protected from light and 7 days under fluorescent room light. Further dilution at 0.05 or 0.5 mg/mL with 0.9% sodium chloride injection (NS), USP, yields a solution that is stable for at least 24 Hours at room temperature. Intact vials in reconstituted solution should be maintained at room temperature. Do not refrigerate and protect unopened container from light.

#### 6.1.3 Preparation

The total dose of cisplatin will be injected into a bag of 0.9% sodium chloride for injection, USP, to make 500 mL of final volume ( $\pm$  10%) prior to administration.

#### 6.1.4 Administration

Cisplatin-100 mg/M {up to 130 mg/M maximum dose} (in 500 mL) will be added to a stable perfusion system.

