In adult studies of carcinomatosis, there were no procedure related mortalities; morbidity included renal impairment, ascites, and pancreatitis. Dose limiting toxicity included grade III leukopenia, grade IV neutropenia and grade III and IV thrombocytopenia at the higher doses only (greater than 800 mg/M). (20, 21) Specifically, no patient had a prolonged postoperative ileus and no adverse effect on wound healing was observed. Following surgery, the median time before tolerating enteral feeds was 5 days (range 1-7 days), and patients could tolerate a regular diet at a median of 7 days (range 4-8 days). Neither patient who had undergone bowel resection and anastomosis followed by HIPEC had any anastomotic complication. One patient suffered a subfascial hematoma incurred from trauma to the left inferior epigastric artery. (20) In the mesothelioma study, the MTD of cisplatin was 300 mg/M. Above this dose there were significant rises in creatinine and one patient required temporary hemodialysis. (21) There have not been any untoward effects of the HIPEC on the ability of these patients to heal incisional wounds and convalesce uneventfully.

This intraoperative treatment using HIPEC in children has provided some very encouraging results. The phase I study of HIPEC in children done here (protocol #2005-0917) proved to be safe. There were no protocol related deaths. Two SAE's included temporary cardiomyopathy likely related to the 4 kg+ tumor resected and supraventricular tachycardia likely related to central venous catheter malposition. Several children had temporary increased creatinine, up to 1.9. However, no problems were seen with urinary output; serum creatinine returned to normal within 1-2 weeks without treatment or dialysis.

Preliminary results suggest 3 year disease free survival is 71% (compared to 26% in historic controls) and disease free interval is increased 5 times from 1.6 to 9 months in the subset of patients with DSRCT. The 2 sarcoma patients died within 6 months and one mesothelioma patient is alive with minimal disease. Another mesothelioma patient in 3rd relapse was treated with surgery + HIPEC is >2 years from surgery. In summary there appears to be benefit in many and we have reached a dose limiting toxicity (DLT), elevated creatinine using HIPEC with cisplatin at 150 mg/M.

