### Rationale

Desmoplastic small round cell tumor (DSRCT) is a rare disease of children, adolescents and young adults, which begins in the abdominal cavity. Less than 200 cases are reported in the world literature. The primary organ of DSRCT origin is the peritoneum. It is a very unique tumor that is difficult to treat because of the infiltrative and diffuse nature of the peritoneum. Patients may present with dozens to hundreds of tumors studding the peritoneal cavity. DSRCT was only recently described in 1991 and since then multimodality treatment including chemotherapy, radiation and aggressive surgery, has not improved outcome. Here at UT MDACC the PI has conducted a phase I trial in children with 'carcinomatosis' who underwent continuous hyperthermic peritoneal perfusion using cisplatin after cytoreductive surgery. (This was an investigator initiated trial and we were the only center in the North America embarking on this effort)

For continuity, we propose to open the phase II study on the subset of patients with the best prognosis after HIPEC, those with DSRCT. In data not yet published, we compared the 9 patients with DSRCT who have undergone HIPEC with 15 historical adolescent and adult patients with DSRCT at UT MDACC who had chemotherapy +/- radiation therapy only and no HIPEC and found a survival advantage of 41 weeks in the patients undergoing HIPEC, a 3 year median survival of 26% for those not undergoing HIPEC and 71% for those who had HIPEC. This is very preliminary data with few patients and follow up is only 1-3 years. Further study of HIPEC in DSRCT is warranted. The surgical study plan and delivery of hyperthermic chemotherapy are the same as the previously approved phase I protocol. The maximum tolerated dose, the safe dose of cisplatin found in phase I, is 100 mg/M. Pediatric and adult patients with other non-carcinoma tumors with extensive peritoneal disease will be eligible if no standard HIPEC treatment has been established for these patients. Results of the research analysis will not be shared with the patient during the conduct of this study nor will the results influence the clinical strategy.

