### 2.0 ELIGIBILITY ASSESSMENT AND ENROLLMENT

#### 2.1 Inclusion Criteria

- 2.1.1 Age greater than or equal to 1 year.
- 2.1.2 Histologically or genetically proven diffuse peritoneal or retroperitoneal tumor from desmoplastic round cell tumor, ovarian germ cell, sarcoma, Wilms' tumor, or other non-carcinoma tumors.
- 2.1.3 Radiologic workup must demonstrate that the disease is confined to the abdominal cavity
- 2.1.4 Radiologic workup or prior abdominal exploration must be consistent with disease which can be debulked to a residual size of less than or equal to 1 cm thickness per tumor deposit
- 2.1.5 Patients must have a minimum expected duration of survival of greater than 6 weeks as determined and documented by the attending surgeon or medical oncologist.
- 2.1.6 Patients must not have any systemic illness which precludes them from being an operative candidate as determined by anesthesia preoperative evaluation. This includes but is not limited to, sepsis, liver failure, pregnant or lactating females.
- 2.1.7 Patients must have fully intact mental status and normal neurologic abilities. Intact mental status is defined by 'the capacity to identify and recall one's identity and place in time and space.' Assessment of mental status and documentation of fully intact mental status will be completed using physical and mental exam by the referring doctor or oncologist.
- 2.1.8 Patients must have adequate renal function (serum creatinine  $\leq$  1.5 mg/dl without history dialysis or renal failure or creatinine clearance less than 50 mL/min/1.73 M if less than 5 years of age)
- 2.1.9 Patients will be eligible if the WBC is  $\geq$ 2000/ $\mu$ l or ANC is  $\geq$ 1,500 and platelets are  $\geq$  100,000/mm^3
- 2.1.10 Patients will be eligible if serum total bilirubin and liver enzymes are  $\leq$  2 times the upper limit of normal
- 2.1.11 Patients must be recovered from any toxicity from all prior chemotherapy, immunotherapy, or radiotherapy and be at least 14 days past the date of their last treatment

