- 3.1.4 HIPEC and Cisplatin- Thirty minutes before HIPEC is begun, body temperature is cooled to 35°C. During the procedure, the cooling blanket and ice packs at the patients head and legs will be adjusted as necessary to maintain core body temperature below 38.5°C (as measured by esophageal probe). The catheters are connected to a perfusion circuit. The perfusate passes from a reservoir through a roller pump, heat exchanger and then into the abdominal cavity. Efflux from a second catheter is then recirculated through the reservoir and pump. The perfusion flow rate will be maintained to distend the abdomen 5 ( $\pm$ 2) liters/minute, and a perfusate volume will be maintained which moderately distends the abdominal cavity. Before the instillation of Cisplatin, the peritoneal cavity is warmed to a target of 40°C ( $\pm$ 1°C) as estimated by the influx/efflux catheter or peritoneal probe and the anesthesiologist will hydrate the patient with isotonic solution. The perfusion is continued for 90 minutes after adding the cisplatin. Cisplatin at 100 mg/M (1mg/1mL concentration in syringes) is to be added to the perfusate. The total maximum dose will not exceed

130 mg. Constant physical manipulation of the abdomen is maintained for the entire 90 minutes to assure even distribution of the perfusate. Peritoneal temperature is measured every 10-15 minutes by up to eight probes placed either beneath the peritoneal surface or at the influx and efflux catheters. At the end of the perfusion, the abdomen is re-opened and the perfusate is again irrigated from the abdominal cavity. The bowel is then thoroughly re-inspected for any perforations incurred and bowel anastomosis are completed. Throughout the procedure urine output must be maintained at 1-2 cc/kg/hr. Post-operative hydration will include 1.5 x maintenance normal saline or lactating ringer and maintenance of urine output of at least 1cc/kg/hr and replacing urine output cc/cc every hour with normal saline, for the first 48 hours to prevent hypovolemia and renal failure.

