4.4 Re treatment criteria

4.4.1 If patients return with recurrent measurable disease and experienced a 6 month disease free interval since the last HIPEC, they will be offered a reperfusion when there is radiographic evidence of recurrent intra-abdominal disease and no new contraindications. Patients having a reperfusion will be treated with 50 mg/M of cisplatin. (This is based on renal insufficiency seen in 2 patients who underwent 2 perfusions at 100 mg/M)

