#### 6.1.5 Toxicities

Cisplatin produces renal tubular toxicity's associated with renal insufficiency and electrolyte, (i.e. magnesium, potassium, calcium, phosphate, carbon dioxide) wasting which may result in significant hypomagnesaemia and hypokalemia. Neurotoxicity manifests as both sensory and motor peripheral neuropathies. Cisplatin is also toxic to the 8th cranial nerve producing ototoxicity which consists of primarily deficits in high frequency auditory acuity, but may include vestibular abnormalities. Systemic administration of cisplatin at doses similar to those planned in this study is associated with significant nausea and thrombocytopenia. Transient moderate elevations of hepatic transaminases and acute systemic allergic reaction including anaphylaxis may also occur. The prior phase I study of HIPEC with heated cisplatin has not identified any regional intraperitoneal toxicity from cisplatin and the dose to be used is 100 mg/M. The heat may cause a prolonged gastroparesis.

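### The cisplatin maximum is 130 mg in section 3.1.4 but 130 mg/M² in section 6.1.4, so the two sections give different doses to any patient above 1.3 M²

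*Combined protocol and SAP*

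**What the plan says.** The planned dose for a first perfusion is consistent: sections 3.1.4, 6.1.4 and 6.1.5 all give 100 mg/M², and the Rationale names the same figure as the phase I maximum tolerated dose.

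The maximum is not consistent:

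- Section 3.1.4 says "The total maximum dose will not exceed" and, after a page break, completes the sentence with 130 mg and a full stop. This is an absolute amount.
- Section 6.1.4 adds in braces, after the 100 mg/M² dose, "up to 130 mg/M 2 maximum dose". This is an amount per unit of body surface.

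Both are current dosing instructions, and neither refers to the other. For repeat perfusions, section 4.4.1 sets a separate dose of 50 mg/M².

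On who may be treated, section 2.1.1 requires only "Age greater than or equal to 1 year" and sets no upper limit. The Rationale makes adults eligible, and sections 4.5.4 and 5.2.1 provide for adult intensive care and adult consent.

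**The concern.** Someone preparing the drug from section 6.1.4 and someone working from section 3.1.4 would arrive at different amounts for the same patient once BSA exceeds 1.3 M². Cisplatin is the nephrotoxic agent in this regimen. The Background reports dose-limiting creatinine elevation at 150 mg/M² in the phase I study, and section 4.4.1 reports "renal insufficiency seen in 2 patients who underwent 2 perfusions at 100 mg/M"² as the reason for halving the repeat dose. Whether an absolute cap applies is therefore a safety question.

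There is also a question of interpretation. With at most 22 patients, the results should describe one regimen. At 2.0 M² the delivered dose could be 65 or 100 mg/M², depending on which section was followed.

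Read literally, the braces in section 6.1.4 also name a ceiling 30% above the maximum tolerated dose (130/100 = 1.30). Nothing in the protocol provides for escalation above 100 mg/M², so that reading is unlikely.

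**Working it through.** **Inputs from the protocol.** Planned dose 100 mg/M² (3.1.4, 6.1.4, 6.1.5). Cap A 130 mg (3.1.4). Cap B 130 mg/M² (6.1.4). Repeat dose 50 mg/M² (4.4.1). Thiosulfate loading dose 7.5 gm/M², maximum 12.5 gm (3.1.6, 6.2.3, 6.2.4).

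**Assumed.** The BSA values; the protocol gives none for its patients.

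**Formulas.**

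- Dose under 3.1.4 = min(100 × BSA, 130) mg.
- Dose under 6.1.4 = min(100, 130) × BSA = 100 × BSA mg.
- Cap A binds when 100 × BSA > 130, that is, above 1.3 M². Cap B never binds.
- Ratio (6.1.4 to 3.1.4) = 1 up to 1.3 M², then 100 × BSA/130 = BSA/1.3.
- Delivered dose per M² under 3.1.4 = 130/BSA above 1.3 M².

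| BSA (M²) | 3.1.4 (mg) | 6.1.4 (mg) | Ratio | 3.1.4 (mg/M²) | 6.1.4 (mg/M²) |
|---|---|---|---|---|---|
| 1.0 | 100 | 100 | 1.00 | 100 | 100 |
| 1.3 | 130 | 130 | 1.00 | 100 | 100 |
| 1.5 | 130 | 150 | 1.15 | 86.7 | 100 |
| 1.8 | 130 | 180 | 1.38 | 72.2 | 100 |
| 2.0 | 130 | 200 | 1.54 | 65.0 | 100 |

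**Repeat perfusion.** 50 × BSA exceeds 130 mg only above 130/50 = 2.6 M². In practice the conflict is confined to the first perfusion.

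**Does the protocol expect patients this large?** Its thiosulfate cap suggests so. That cap binds only above 12.5/7.5 = 1.67 M², where the cisplatin doses already differ: 130 against 167 mg, a ratio of 1.28. The thiosulfate cap is an absolute amount and is identical wherever it appears. The Background also describes desmoplastic small round cell tumor as a disease of ages 5 to 30, 90% male.

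**Thiosulfate cover.** Below both caps the loading dose is 7,500/100 = 75 mg per mg of cisplatin. At 2.0 M² the capped 12,500 mg gives 12,500/130 = 96 mg per mg under 3.1.4, but 12,500/200 = 62.5 mg per mg under 6.1.4. The maintenance infusion has no cap.

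**The case against.** The strongest reply is that the two limits can be obeyed together. A dose of min(100 × BSA, 130) mg breaks neither, whereas 180 mg at 1.8 M² breaks section 3.1.4, which is categorical. On this view the doses diverge only if section 6.1.4 is read alone. That is correct. But section 6.1.4 is the administration instruction in the pharmaceutical part of the protocol. Following it as written breaches section 3.1.4 for any patient above 1.3 M², and nothing in it warns the reader.

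Second, the higher reading still gives no more than 100 mg/M², which the protocol regards as the safe phase I dose and which is below the 150 mg/M² where toxicity was dose-limiting. This also stands, and it limits the harm. The protocol does not say whether the phase I dose was itself capped or why 130 mg was chosen, so the added risk of uncapped dosing cannot be judged from the documents.

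Third, the renal insufficiency in section 4.4.1 followed two perfusions and has already been met by halving the repeat dose. It is therefore only indirect evidence about a first perfusion.

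Fourth, safeguards apply under either reading: thiosulfate, hydration and urine-output targets, postoperative creatinine checks, and a stopping rule that counts renal events. A single investigator performs every perfusion (section 5.1), which makes divergence in the operating room less likely, though not a misreading in pharmacy.

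**Conclusion.** The inconsistency is real and sits in operative dosing text, so it must be corrected. The doses are identical up to 1.3 M². Above that they differ by a factor of BSA/1.3, or 1.15 to 1.54 between 1.5 and 2.0 M². How many patients are affected is unknown because BSA is not reported, but eligibility plainly admits adolescents and adults of this size.

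The most likely explanation is a unit slip in section 6.1.4, since a 130 mg/M² limit on a 100 mg/M² dose serves no purpose. That is an inference. No endpoint, stopping boundary or operating characteristic in Tables 1 and 2 changes. The consequence is for dosing safety and for knowing what dose was studied.

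**What to change.** Amend section 6.1.4 to give 100 mg/M² up to a total maximum dose of 130 mg, matching section 3.1.4. If the sponsor intends no absolute cap, that should be an explicit, justified decision, with the cap removed from both sections.

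As a secondary step, tabulate the delivered cisplatin dose in mg/M² for each patient, because under the 130 mg cap anyone above 1.3 M² receives less than 100 mg/M².

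The cost is a one-line protocol correction and one descriptive column. No further patients, procedures or inferential analyses are needed.

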#### 6.1.5 Toxicities

Cisplatin produces renal tubular toxicity's associated with renal insufficiency and electrolyte, (i.e. magnesium, potassium, calcium, phosphate, carbon dioxide) wasting which may result in significant hypomagnesaemia and hypokalemia. Neurotoxicity manifests as both sensory and motor peripheral neuropathies. Cisplatin is also toxic to the 8th cranial nerve producing ototoxicity which consists of primarily deficits in high frequency auditory acuity, but may include vestibular abnormalities. Systemic administration of cisplatin at doses similar to those planned in this study is associated with significant nausea and thrombocytopenia. Transient moderate elevations of hepatic transaminases and acute systemic allergic reaction including anaphylaxis may also occur. The prior phase I study of HIPEC with heated cisplatin has not identified any regional intraperitoneal toxicity from cisplatin and the dose to be used is 100 mg/M. The heat may cause a prolonged gastroparesis.

## 6.2 Sodium Thiosulfate

### 6.2.1 Formulation

Sodium thiosulfate injection, USP, is commercially available as a sterile nonpyrogenic solution of sodium thiosulfate dissolved in water for injection, USP, at concentrations of 10% (100 mg/mL) at 25% (250 mg/mL). The commercial formulation may also contain boric acid and sodium hydroxide to adjust the pH to 8.5 – 9.0.

### 6.2.2 Stability and Storage

Manufacturer's expiration date is present on the commercial formulation.

### 6.2.3 Preparation

A loading dose of 7.5 gm/M (maximum 12.5 gm) of sodium thiosulfate will be diluted in 20 mL/kg of 0.9% normal saline up to 500 mL. An additional dose of sodium thiosulfate 1.275 gm/M/hr for 12 hours will be diluted in 0.9% normal saline for maintenance infusion.

### 6.2.4 Administration

Sodium thiosulfate will be administered by a loading dose and then a 12 hour continuous intravenous infusion. A loading dose of 7.5 gm/M (maximum 12.5 gm) of sodium thiosulfate will be diluted in 20 mL/kg of 0.9% normal saline up to 500 mL. This loading dose will be infused over 20 minutes beginning 30 minutes ( $\pm$  15 minutes) after the addition of cisplatin to the peritoneal perfusion circuit. Then maintenance infusion of sodium thiosulfate 1.275 gm/M/hr for 12 hours will be delivered by infusion pump.

### 6.2.5 Toxicities

Other than osmotic disturbances, sodium thiosulfate is well tolerated in humans. Large orally administered doses are associated with a cathartic effect. In preclinical studies in dogs continuous intravenous administration of sodium thiosulfate has produced hypokalemia presumably due to an osmotic diuretic effect.

**Appendix 1  
 Clinical and Laboratory Follow up**

	Eval. days	Baseline (Pre-op)	D1	D2	D3	D4	D5	D11	D14	D30	3mo	6mo
Labs/ Tests												
Hb		X	X	X	X	X	X	X	X	X	X	X
Hct		X	X	X	X	X	X	X	X	X	X	X
Plt		X	X	X	X	X	X	X	X	X	X	X
Na		X	X	X	X	X	X	X	X	X	X	X
K		X	X	X	X	X	X	X	X	X	X	X
Cl		X	X	X	X	X	X	X	X	X	X	X
CO 2		X	X	X	X	X	X	X	X	X	X	X
BUN		X	X	X	X	X	X	X	X	X	X	X
Cr		X	X	X	X	X	X	X	X	X	X	X
Mg ++		X	X	X	X	X	X	X	X	X	X	X
Ca ++		X	X	X	X	X	X	X	X	X	X	X
Alb		X	X	X	X	X	X	X	X	X	X	X
PO 4		X	X	X	X	X	X	X	X	X	X	X
AST		X	X	X	X	X	X	X	X	X	X	X
ALT		X	X	X	X	X	X	X	X	X	X	X
Alk Phos		X	X	X	X	X	X	X	X	X	X	X
PT/PTT		X										
TB		X	X	X	X	X	X	X	X	X	X	X
Amy		X	X	X	X	X	X	X	X	X	X	X
PE		X	X	X	X	X	X	X	X	X	X	X
ECG		X										
Echo		X										
CT scan			X*								X	X
MRI			X*								X	X
Audio			X							X		
AE			X	X	X	X	X	X	X	X	X	X
PK			X									
Preg.			X									
24-hr UCr			X**									

\*Choose one or both as clinically indicated. May include PET-CT. TB=total bilirubin, Audio=audiology, AE adverse events evaluation, PK= pharmacokinetic cisplatin level at 24 hours, Preg.=pregnancy test (blood or urine), Alb=Albumin, D=post op day

\*\*24 hour urine collection for creatinine clearance calculation for children <5 years old

Optional PK Testing					
	0 (pre-perfusion)	30 min	60 min	90 min	24-hr (post-op)
Blood	X	X	X	X	X
Peritoneal Fluid	X	X	X	X	X

